**9. How satisfied are you with the instruction given by doctor about pain control?**

- A. Very satisfied [ ]
- B. Satisfied [ ]
- C. Neither satisfied Nor dissatisfied [ ]
- D. Dissatisfied [ ]
- E. Very Dissatisfied [ ]

**10. How satisfied are you about the waiting times to see doctors in the clinic?**

- A. Very satisfied [ ]
- B. Satisfied [ ]
- C. Neither satisfied Nor dissatisfied [ ]
- D. Dissatisfied [ ]
- E. Very Dissatisfied [ ]

---

**11. How short or long on the next clinic appointment giving by the doctors?**

- A. Very short [ ]
- B. Short [ ]
- C. Neither short Nor long [ ]
- D. Long [ ]
- E. Very long [ ]

**12. How satisfied are you about the services provided in the lab?**

- A. Very satisfied [ ]
- B. Satisfied [ ]
- C. Neither satisfied Nor dissatisfied [ ]
- D. Dissatisfied [ ]
- E. Very Dissatisfied [ ]

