## 3. Objectives

### 3.1. Primary objective

To assess the needs of SCD patients and health workers, with particular reference to the disease management in the clinical centre.

The study is intended as a pilot experience to verify the feasibility of the action through a structured survey. This is a descriptive, mixed method prospective questionnaire-based study. The study is intended as a pilot experience to verify the feasibility of the action through a structured survey.

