### SECTION A

#### Bio Data

1. State \_\_\_\_\_
2. Local Government \_\_\_\_\_
3. Name of SCD Clinic/Hospital \_\_\_\_\_
4. Age \_\_\_\_\_
5. Gender Male [ ] Female [ ]
6. Education: University [ ], Secondary [ ], Primary [ ], Nursery [ ] Other (please specify) \_\_\_\_\_
7. Occupation: Business [ ], Civil Servant, [ ], Farmer [ ], Other (please specify) \_\_\_\_\_

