**13. How satisfied are you during or when communicating with lab technicians?**

- A. Very satisfied [ ]
- B. Satisfied [ ]
- C. Neither satisfied Nor dissatisfied [ ]
- D. Dissatisfied [ ]
- E. Very Dissatisfied [ ]

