**14. How satisfied are you about the waiting times in the lab?**

- A. Very satisfied [ ]
- B. Satisfied [ ]
- C. Neither satisfied Nor dissatisfied [ ]
- D. Dissatisfied [ ]
- E. Very Dissatisfied [ ]

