**22. Do you need to move to other centres to perform one of the following?**

- A. Periodical visit [ ]
- B. Specialist visit [ ]
- C. Special examination [ ]

D. Laboratory analysis [ ]  
E. Other (please specify) \_\_\_\_\_

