**24. Are there facilities for psychological support in this hospital?**

A. Yes [ ]  
B. No [ ]

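### Annex I items 12-14 ask for ratings of an unnamed laboratory with no opt-out, although item 22 allows for laboratory tests at another centre, so some ratings may be attributed to the wrong laboratory

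*Protocol*

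**What the plan says.** The study assesses needs "with particular reference to the disease management in the clinical centre" (Protocol, section 3.1). Annex I, Section B, has three consecutive laboratory items:

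- Item 12: "How satisfied are you about the services provided in the lab"
- Item 13: "How satisfied are you during or when communicating with lab technicians"
- Item 14: "How satisfied are you about the waiting times in the lab"

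Each offers the same five grades from very satisfied to very dissatisfied. There is no box for a laboratory that is not used, and no skip instruction.

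Eight questions after item 14, item 22 asks "Do you need to move to other centres to perform one of the following" and lists, among other options, "D. Laboratory analysis". The only site recorded on the form is in Section A, item 3: "Name of SCD Clinic/Hospital". Some other items point explicitly to the respondent's own hospital, such as item 24: "Are there facilities for psychological support in this hospital".

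Under section 5.1 the investigator gives instructions, but respondents complete the form themselves in private. Section 5.4 names the analysis software and the qualitative method. It gives no rule for assigning laboratory ratings to a centre.

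**The concern.** Three of the twelve Annex I items that open by asking how satisfied the respondent is concern the laboratory. They can describe management in the centre only if the laboratory rated is the centre's own. Through item 22 the form itself provides for respondents who go elsewhere for laboratory analysis, yet items 12-14 give them no way to say so.

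Such a respondent may rate the outside laboratory, rate the centre's laboratory from limited or no use, or leave the item blank. The completed form does not show which of the first two happened or why an item is blank. A centre that sends patients out because it cannot do a test has a clear laboratory need, and its laboratory ratings could look better or worse than its own service deserves.

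The pilot is meant to test the structured survey before a wider one (sections 3.1 and 3.2), so an item left unclear now could be carried forward. Misattribution does not shrink as the sample grows.

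**Working it through.** **Inputs from the Protocol.** Section 3.2 gives 30 patients or parents per centre, and section 3.3 lists four centres: 4 × 30 = 120, which reproduces the stated total. No power or effect-size figure is involved.

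**Step 1: does the form identify the laboratory rated?**

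- Items 12-14 name neither a laboratory nor a hospital.
- Section A records one clinic or hospital per form, so that is the only site to which a rating can be linked.
- Item 22D records a need to go elsewhere for laboratory analysis. It does not say whether all tests or only some are done there. A respondent who ticks it may also use the centre's laboratory and be rating that one.
- Item 22 has no box for *no*, so a blank may mean no need or no answer. It also lacks the instruction in item 21 to tick every option that applies, so 22D may be under-ticked.

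A cross-tabulation by 22D can therefore flag respondents whose rating is uncertain, but it cannot establish which laboratory they rated.

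**Step 2: how much could it matter?** Let *f* be the share of a centre's respondents who rate an outside laboratory, and *d* the difference in the proportion satisfied (or dissatisfied) between the outside and own laboratories. Then

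recorded proportion = (1 − *f*) × own + *f* × outside, so shift = *f* × *d*.

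The documents give neither *f* nor *d*. Both are assumptions here, shown over a range. The shift is in percentage points and takes the sign of *d*:

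| *f* (of 30) | *d* = 10 | *d* = 20 | *d* = 40 |
|---|---|---|---|
| 0% (0) | 0 | 0 | 0 |
| 10% (3) | 1 | 2 | 4 |
| 20% (6) | 2 | 4 | 8 |
| 30% (9) | 3 | 6 | 12 |
| 50% (15) | 5 | 10 | 20 |

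To illustrate the direction, suppose dissatisfaction is 40% for the own laboratory and 10% outside. With *f* = 10%, 20% and 50%, the recorded figure is 0.40 × 0.9 + 0.10 × 0.1 = 37%, 0.40 × 0.8 + 0.10 × 0.2 = 34%, and 0.40 × 0.5 + 0.10 × 0.5 = 25%. Swap the two laboratories and a true 10% is recorded as 13%, 16% and 25%.

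**Step 3: scale.** The 95% half-width at a proportion of 0.5 is 1.96 × √(0.25/30) = 17.9 points for one centre and 1.96 × √(0.25/120) = 8.9 points for all four pooled. For one centre, only the most extreme cell (20 points) exceeds sampling error. If the same *f* and *d* held in every centre, three cells (10, 12 and 20 points) would exceed the pooled half-width.

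**The case against.** The strongest reply is that context already settles the meaning. Respondents have attended the centre for at least six months, and Section A asks for their clinic or hospital. Items 12-14 sit between clinic items, and the objective is framed around the centre. The focus-group guide (Annex III) couples clinic and laboratory straight after two prompts about the respondent's own clinic. The investigator also explains the form. All of this stands, and the centre's own laboratory is the likelier intended reading. But on that reading, someone who does not use the centre's laboratory has no valid answer, so the missing opt-out remains a gap.

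It is also fair that the laboratory items are not unusual in their wording. Items 10, 15 and 18 refer to the clinic or hospital just as generically, and items 16 and 19 name no place at all. Only items 24 and 26 point explicitly to the respondent's own hospital. What sets the laboratory items apart is that item 22D expressly allows for the service to be obtained elsewhere.

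Third, a need to go elsewhere is captured by 22D, by the focus-group prompt on laboratory facilities and by the closing free-text question. That reduces the harm, since a centre's lack of tests need not go unnoticed. It does not make the ratings in items 12-14 interpretable, and no later analysis plan can recover what the form does not collect.

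A reader might infer that respondents tested elsewhere will rate the outside laboratory and that their ratings are counted against the study hospital. The documents do not support that. Item 22D does not show exclusive use of an outside laboratory, and the Protocol states no attribution rule.

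**Conclusion.** The point holds as a minor defect of the instrument. Items 12-14 do not identify the laboratory and offer no non-user answer, while item 22D provides for testing elsewhere. Some ratings may therefore be attributed to the study hospital when they describe another laboratory, and the form cannot show which.

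No bias has been demonstrated. A shift of 1-20 points in a centre's proportion rests on assumed values: 10-50% of respondents rating an outside laboratory and a gap of 10-40 points. It can go in either direction, and it is zero if nobody rates an outside laboratory or the laboratories do not differ. A reader might suppose that the error always flatters a weak centre. That would require outside laboratories to be rated better, and nothing in the documents says so. Over most of the assumed range the shift is smaller than the sampling error for one centre of 30.

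**What to change.** - Reword items 12-14 so that each refers to *the laboratory of this hospital*.
- Add one box before item 12: *I do not use this hospital's laboratory - go to item 15*.
- Report items 12-14 among users, with the number of users stated, and report the non-user share for each centre alongside item 22D. The two overlap but are not the same: a respondent may use the centre's laboratory and still need some tests elsewhere.

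If forms have already been completed in the present wording, tabulate items 12-14 by item 22D and state that the laboratory rated is not known.

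The cost is three wordings and one tick box. The downside is fewer than 30 raters per centre on these items if some respondents are non-users. With 3, 6 or 15 non-users, 27, 24 or 15 raters remain. The half-width 1.96 × √(0.25/n) then rises from 17.9 points to 18.9, 20.0 or 25.3. That is a fair price for ratings that refer to a known laboratory.

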**13. How satisfied are you during or when communicating with lab technicians?**

- A. Very satisfied [ ]
- B. Satisfied [ ]
- C. Neither satisfied Nor dissatisfied [ ]
- D. Dissatisfied [ ]
- E. Very Dissatisfied [ ]

**14. How satisfied are you about the waiting times in the lab?**

- A. Very satisfied [ ]
- B. Satisfied [ ]
- C. Neither satisfied Nor dissatisfied [ ]
- D. Dissatisfied [ ]
- E. Very Dissatisfied [ ]

**15. How satisfied are you with the nursing care in clinic?**

- A. Very satisfied [ ]
- B. Satisfied [ ]
- C. Neither satisfied Nor dissatisfied [ ]
- D. Dissatisfied [ ]
- E. Very Dissatisfied [ ]

**16. How satisfied are you during or when communicating with nurses?**

- A. Very satisfied [ ]
- B. Satisfied [ ]
- C. Neither satisfied Nor dissatisfied [ ]
- D. Dissatisfied [ ]
- E. Very Dissatisfied [ ]

---

**17. How satisfied are you with your/your child SCD current treatment and management for SCD (e.g. Hydroxyurea, blood transfusion, pain medications, vaccination, surgeries etc.)?**

- A. Very satisfied [ ]
- B. Satisfied [ ]
- C. Neither satisfied Nor dissatisfied [ ]
- D. Dissatisfied [ ]
- E. Very Dissatisfied [ ]

**18. How expensive about the cost of treatment in the hospital?**

- A. Very expensive [ ]
- B. Expensive [ ]
- C. Neither expensive Nor inexpensive [ ]
- D. Cheap [ ]
- E. Very cheap [ ]

**19. How good about the about the overall service quality?**

- A. Very good [ ]
- B. Good [ ]
- C. Neither good Nor poor [ ]
- D. Poor [ ]
- E. Very poor [ ]

**20. How would you rate access to the treatment centre (in terms of distance, cost etc.)?**

- A. Very easy [ ]
- B. Easy [ ]
- C. Neither easy nor difficult [ ]
- D. Difficult [ ]
- E. Very difficult [ ]

**21. Who pays for your treatment? (tick all that apply)**

- A. My self/my family [ ]
- B. Health insurance (private) mine [ ]
- C. Health insurance (private) my employer's [ ]
- D. State goverment provide free healthcare [ ]
- E. Other (please specify) \_\_\_\_\_

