### 3.2. Sample size determination

As pilot experience, the questionnaires will be administered to 30 SCD patients or parents/legally designated representatives of children affected by SCD and 30 Professionals working with SCD patients (mainly doctors and nurses) in each centre for a total of 120 patients and 120 health workers. A focus group discussion will be run with the SCD patients/parents. Following the pilot study, a wider survey will be launched involve patients, parents and healthcare professionals in the whole country and in other centres involved in the project.

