## 4. Inclusion and exclusion criteria

The following inclusion criteria will apply for patients/parents:

- Aged  $\geq 18$
- Have SCD diagnosis or having a child with a SCD diagnosis
- Attending the centre from at least 6 months
- Nigerian nationality
- Informed Consent signed

The following inclusion criteria will apply for healthcare professionals:

- Working in a SCD clinic
- At least 5 years of experience with SCD patients
- Informed Consent signed

The following exclusion criteria will apply for all participants:

- Informed consent form withdrawal
- Illiterate subjects
- Any psychiatric conditions impairing the participation in this study.

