## 5. Study procedure

### 5.1. Questionnaire completion

After obtaining the informed consent, subjects (patients, parents/legally designated representatives and healthcare professionals) will be asked to complete the questionnaire. Two questionnaires have been developed, one addressed to patients, parents, legally designated representatives (Annex I) and another one for healthcare professionals (Annex II)

The following measures will be adopted to reduce the interviewer effect:

- The investigator will give instructions to complete, but questionnaires will be self-completed.
- Participants will have time to complete the questionnaire in a private setting.
- Completed questionnaires will be blindly deposited in a closed box. This will be thus safeguarded by the investigators.
- Completed questionnaires will be returned to the coordinating investigator for analysis.

Questionnaires will be pseudonymised: an alphanumeric code will be indicated on each questionnaire and reported on the corresponding informed consent form.

All the study investigators are researchers/officers in the centres not involved in patients' clinical management. The veracity and consistency of responses are of paramount importance for the

---

validity of the study and the improvement of the management of SCD patients: all the actions necessary to allow the participants to freely express themselves will be adopted.

Together with the questionnaire, participants will receive information about the time and venue for the focus group discussion (Annex III). For those who are willing, reminders about the focus group will be sent by e-mail/phone.

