### **5.2. Focus group**

A 45-60 minutes discussion will be scheduled with patients and parents, according to details given in the attached guidance. The principal investigator of each centre will lead the focus group discussion, leaving the possibility to everyone to freely express his/herself.

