### SECTION B

- 1. If you are a patient, what is your diagnosis? If you are a parent, what is the diagnosis of your child?**
  - A. Sickle cell disease [ ]
  - B. Sickle cell/b-thal [ ]
  - C. Sickle Beta-Plus Thalassemia [ ]
  - D. Other (please specify) \_\_\_\_\_
- 2. How is your/your child current transfusion regime?**
  - A. I am not transfused [ ]
  - B. I am regularly transfused [ ]
  - C. I am occasionally transfused [ ]
  - D. Other (please specify) \_\_\_\_\_
- 3. Where do you usually get information about Sickle Cell Disease?**
  - A. Websites
  - B. Social Networks
  - C. Scientific journals
  - D. TV
  - E. Radio
  - F. Leaflets/booklets
  - G. Doctor/nurse
  - H. Other patients
  - I. Relatives/friends
  - J. Religious leaders
  - K. Other (please specify) \_\_\_\_\_

---

**4. Please, indicate your main information source:** \_\_\_\_\_

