### Annex III. FOCUS GROUP INTERVIEW GUIDE

**Topic: Needs Assessment of patients and health workers involved in SCD management.**

**Introduction:**

Hello and welcome to our session. My name is [name], a researcher from **“African Research and Innovative initiative for Sickle cell Education: Improving Research Capacity for Service Improvement” (ARISE)** project, assisting me is .....

Thank you for taking your time to join us to talk about the needs assessment of patients involved in SCD management.

The aim of this discussion is to understand the needs of patients involved in SCD management. We will be discussing on your perceptions and understanding. The discussion will last from 45 minutes to one hour.

As part of the focus group, facilitators will ask questions related to your own perception on health workers and the facilities involved in SCD management. In order to have a fruitful discussion, participants are encouraged to speak one person at a time. Please you are to keep in mind that there are no “negative or positive” comments to any question that will be asked. The purpose is to stimulate conversation and hear the opinion of everyone in this room. I hope you will be comfortable speaking honestly and sharing your ideas with us.

Please note that this session will be recorded, and notes will be taken during the focus group to ensure that we don't miss any of your comments due to their importance. Unfortunately, we can't write fast enough to get them all down that is why we must record them. However, the comment from the focus group will remain confidential and your name will not be attached to any comment. Do you have any question before we begin? Thank you.

1. Please share with me your perception of the health workers in this clinic.
2. Please share with me your perception of the services provided in this clinic.
3. Please share with me your perception of the facilities both in the clinic and lab (e.g. adequacy and functioning).
4. What do you perceive as major need concerning the management of your disease in the clinic?
5. What is the most satisfactory aspect of the management of your disease in the clinic?
6. Is there anything we haven't discussed that you think is important regarding the needs of patients involved in SCD management?

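### Annex I item 21 and the answer options of item 2 do not make clear that a parent should answer for the child, so payer and transfusion answers may be ambiguous (minor)

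*Protocol*

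**What the plan says.** Protocol section 4 admits adults who "Have SCD diagnosis or having a child with a SCD diagnosis". Section 3.2 gives each centre "30 SCD patients or parents/legally designated representatives of children affected by SCD", a combined quota with no split between patients and parents. Section 5.1 describes two questionnaires, "one addressed to patients, parents, legally designated representatives (Annex I", the other for health professionals. Parents and representatives therefore fill in the same form as patients.

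In Annex I, Section B:

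- Item 17 asks "How satisfied are you with your/your child SCD current treatment and management for SCD".
- Item 21 asks "Who pays for your treatment? (tick all that apply" with no mention of a child.
- Item 2 asks about the regimen of the respondent or the child. Its three closed options are all in the first person, the first being "I am not transfused". The fourth is free text.

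Section 5.2 states: "A 45-60 minutes discussion will be scheduled with patients and parents". In the interview guide (Annex III), question 4 reads "What do you perceive as major need concerning the management of your disease in the clinic", and question 5 also refers only to the participant's own disease.

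**The concern.** When one form serves two kinds of respondent, each item has to make clear whose situation is being reported. Item 21 does not. A parent could report who pays for the child's sickle cell care or who pays for the parent's own care. In item 2 the stem and the options disagree: an untransfused parent of a regularly transfused child can tick the first option and be literally truthful.

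The two items matter because they stand alone. Item 18 asks how expensive care is, but only item 21 asks who bears the cost. Item 17 mentions transfusion as an example of treatment, but only item 2 records the regimen. The primary objective is to assess needs, and section 3.2 plans a wider survey after this pilot, so an ambiguity left in the form could be carried forward.

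**Working it through.** The protocol gives no figure to reproduce. The check is a comparison of wording, followed by a count of the forms exposed.

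**1. Wording side by side (Annex I, Section B)**

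| Item | Child named in stem? | Answer options | Result for a parent |
|---|---|---|---|
| 17 (satisfaction with treatment) | Yes | Satisfaction scale | Clear that the child's treatment is meant |
| 21 (who pays) | No | Payer or source of the policy | Not stated whose treatment |
| 2 (transfusion) | Yes | First person in A to C, free text in D | Stem and options do not match |

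Items 17 and 21 both concern treatment, and only item 17 names the child.

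**2. Is a missing reference to the child a cue to answer for oneself?**

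The stems of items 1, 2, 6, 7, 8, 17 and 27 name the child, which is 7 of 27. The other 27 − 7 = 20 do not. Several of those 20 concern care that a parent would naturally describe for the child: item 9 (instruction on pain control), item 22 (visits, examinations and laboratory work elsewhere) and item 25 (psychological support). The form has no firm convention, so item 21 leaves the parent to guess. It does not direct the parent to answer for himself or herself.

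**3. Can the ambiguity be resolved later?**

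- Section A has no field for respondent type, and its age and gender items do not say whose they are.
- Item 1 addresses both groups, but its options record only a diagnosis.
- Under section 5.1 forms are completed privately and put in a closed box. No check of the answers with the respondent is described.
- The questionnaire code also appears on the consent form. If the consent form shows the signatory's capacity, respondent type might be recovered that way. It would still not show whom a parent's tick described.

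**4. How many forms are exposed?**

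Patient/parent forms: 30 per centre × 4 centres = 120. With a parent share p, the exposed forms number 120 × p. The protocol does not fix p, so the range is 0 to 120. Assumed shares of 25%, 50% and 75% give 120 × 0.25 = 30, 120 × 0.50 = 60 and 120 × 0.75 = 90.

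These are forms on which the ambiguity exists, not wrong answers. The number of wrong answers is 120 × p × m, where m is the proportion of parents who answer for themselves and whose answer differs from the child's. The documents say nothing about m. It can be well below the rate of misreading: a family that pays out of pocket for both parent and child gives the same tick either way.

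**The case against.** The strongest reply is that context settles the meaning. The form is titled as a needs assessment in sickle cell disease. The items before item 21 concern treatment of that disease, its cost in the hospital and access to the treatment centre. A parent without the disease has no treatment of his or her own in that sequence. The stem of item 2 already tells the parent whose regimen is meant. The insurance options in item 21 name whose policy pays, not who is treated, so a parent whose own policy covers the child is right to tick them. Investigators also give instructions on completing the form, although the protocol does not state their content. All of this stands, and it reduces the problem to avoidable ambiguity.

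A reader might infer more: that parents will report their own payer and their own transfusion status, or that the focus groups are biased because questions 4 and 5 speak only of the participant's own disease. The documents do not support either. Items 2 and 21 can both be read correctly. The focus group is a live discussion led by the centre's principal investigator, so a parent's doubt can be settled on the spot. A parent without the disease can hardly answer questions 4 and 5 except about the child. Question 6 also asks about patients' needs in neutral terms, and Annex I closes with an open question on improving management.

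Context does not remove the defect in the written form. Item 21 still fails to say whose treatment is meant, the options of item 2 still contradict its stem, and no step in the procedure checks what a parent meant.

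**Conclusion.** The point holds as a minor defect of the questionnaire. Items 21 and 2 leave it open whether a parent's answer describes the parent or the child, so the payer and transfusion distributions may contain misclassified answers.

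For item 2 the direction can be stated: an untransfused parent of a transfused child who answers for himself or herself moves a record from transfused to not transfused. For item 21 the direction is not determined, because several boxes may be ticked and a parent's cover may or may not extend to the child.

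No size can be given. A reader might be tempted to state a shift in percentage points, but that would multiply an assumed parent share by an assumed misreading rate, and neither has a source in the documents. The study is a descriptive pilot, and the protocol ties no test or decision rule to either item. The conclusion rests on the text of Annex I and on parents being intended respondents. It has no practical effect at a centre that enrols no parents or representatives.

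**What to change.** Two changes to Annex I:

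- Item 21: ask who pays for *your/your child's SCD treatment*, in line with item 17.
- Item 2: make the options impersonal: *Not transfused*, *Regularly transfused*, *Occasionally transfused*, *Other (please specify)*.

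A tick box for respondent type would not replace these edits, because a parent's answer could still describe either person.

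Optionally, for consistency, let Annex III questions 4 and 5 refer to *your (or your child's) disease*. This is an editorial alignment, not a correction of measurable bias.

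The cost is a few words in the annexes, with no added items, participants or completion time. The same wording should go into the form used for the wider survey. If forms have already been completed, the wording cannot be repaired in the analysis, and the report should state the ambiguity as a limitation of these two items.
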